### **6.1.3. Prior Therapies for Atopic Dermatitis**

Prior medications for AD will be coded using the WHO Drug Dictionary and summarized by treatment group for the ITT population. The type of treatment and reason for discontinuation will be summarized as well. Prior nondrug therapies for AD will be listed.

### **6.1.4. Medical History**

For participants in the ITT population during the VC period, medical history will be summarized by assigned treatment groups. This summary will include the number and percentage of participants with medical history for each body system/organ class as documented in the eCRF.

## **6.2. Disposition of Participants**

The number and percentage of participants who were randomized, treated, and completed the VC period and of participants who discontinued treatment or withdrew from the study during the VC period with a primary reason for discontinuation will be summarized for the ITT population during the VC period.

The number and percentage of participants who were treated and completed the VCE DB period and escape arm, were ongoing treatment during the VCE DB period and escape arm, and discontinued treatment or withdrew from the study during the VCE DB period and escape arm with a primary reason for discontinuation will be summarized for the participants who entered VCE period. The number and percentage of participants who entered the escape arm during the VCE DB period will be summarized as well.

### 6.3. Protocol Deviations

In general, the following are important Protocol deviations that may significantly affect the primary analysis:

- Missing data for the coprimary endpoint
- Overall application compliance less than 80% during the VC period
- Did not apply any study cream in the VC period
- IGA assessment outside the 14-day window for the Week 8 (Day  $57 \pm 7$ ) visit.

Participants with any of the deviations listed above will be excluded from the PP population. In addition, important Protocol deviations, such as those related to inclusion/exclusion criteria, discontinuation criteria, and use of prohibited concomitant medications, will be reviewed. Decisions as to whether any of these deviations warrant exclusion from the PP population will be made prior to unblinding.

Protocol deviations will be summarized by treatment groups in the VC, VCE DB, and escape arm in the VCE periods separately.

### 6.4. Exposure

For participants in the safety population during the VC period, VCE primary population in the VCE DB period, and VCE escape population for the participants who entered escape arm, descriptive statistics will be provided (ie, by treatment group for duration of treatment, average daily amount of cream applied [g] and total amount of cream applied [g]). Duration of treatment with ruxolitinib cream or vehicle cream is defined as the number of days from Day 1 to the last record of ruxolitinib cream or vehicle cream application in the specific period.

### 6.5. Study Drug Compliance

Overall compliance (%) for the application of ruxolitinib cream or vehicle cream during the VC period will be calculated for all participants in the safety population as follows:

$$\text{Overall application compliance (\%)} = 100 \times [\text{total number of nonmissing applications}] / [\text{total number of intended applications}],$$

where the total number of nonmissing applications is the total number of applications that the participant actually applied during the study. The total number of intended applications is the number of planned applications minus the number of interrupted applications.

### 6.6. Prior and Concomitant Medications

For participants in the ITT population during the VC period, prior and concomitant medications will be coded using the WHO Drug Dictionary and summarized as number and percentage of participants with prior and concomitant therapies by WHO drug class and WHO drug term. For participants in the VCE period, only concomitant medications will be summarized. Concomitant medications for AD will also be summarized by treatment groups in the VC and VCE periods.

## 7. EFFICACY

[Appendix A](#) provides a list of planned tables, figures, and listings. Sample data displays are included in a separate document.

### 7.1. General Considerations

For all continuous variables, both the actual value and change and/or percentage from baseline (if available) will be analyzed.

All by-visit analyses will include the safety follow-up period if the data are available.

### 7.2. Efficacy Hypotheses

See Section [3.2](#) for the efficacy hypotheses that will be tested in this study.

### 7.3. Analysis of the Primary Efficacy Parameters

#### 7.3.1. Primary Efficacy Measures

The coprimary endpoints are:

- Proportion of participants with EASI75 from baseline at Week 8.
- Proportion of participants with IGA-TS at Week 8.

##### 7.3.1.1. Eczema Area and Severity Index Score

Atopic dermatitis will be assessed using the EASI scoring system, which is a validated scoring system that grades the physical signs of AD to provide a measure of AD severity (ranging from 0 to 72).

The weight of the body regions for the EASI scoring is as follows:

head/neck (H) = 0.1, upper limbs (UL) = 0.2, trunk (T) = 0.3, and lower limbs (LL) = 0.4.

Each of the 4 body regions is assessed separately for erythema (E), induration/papulation/edema (I), excoriations (Ex), and lichenification (L) for an average degree of severity of each sign in each region with 0 = none, 1 = mild, 2 = moderate, and 3 = severe, with half-steps allowed.

The disease severity strata for the EASI are as follows: 0 = clear; 0.1 to 1.0 = almost clear; 1.1 to 7.0 = mild; 7.1 to 21.0 = moderate; 21.1 to 50.0 = severe; 50.1 to 72.0 = very severe.

The categorical variable EASI75 to indicate the EASI responder will be set to 1 for percentage improvement from baseline in EASI score of 75% or greater and will be equal to 0 for percentage improvement of less than 75%. The EASI50 and EASI90 are defined with the same pattern.

##### 7.3.1.2. Investigator's Global Assessment

The IGA is an overall eczema severity rating on a 0 to 4 scale that will be assessed during site visits. The grades for the IGA are shown in [Table 3](#).

**Table 3: Investigator's Global Assessment**

Grade	Severity	Status
0	Clear	No erythema or induration/papulation, no oozing/crusting; there may be minor residual discoloration
1	Almost clear	There may be trace faint pink erythema, with almost no induration/papulation, and no oozing/crusting
2	Mild	There may be faint pink erythema, with mild induration/papulation and no oozing/crusting
3	Moderate	There may be pink-red erythema with moderate induration/papulation and there may be some oozing/crusting
4	Severe	There may be deep or bright red erythema with severe induration/papulation and with oozing/crusting

Source: [FDA 2022](#).

The IGA-TS is defined as an IGA score of 0 or 1 with  $\geq 2$ -grade improvement from baseline.

### 7.3.2. Primary Efficacy Analyses

The primary analysis will be based on the ITT population in the VC period. The primary alternative hypothesis (superiority of ruxolitinib 1.5% cream BID compared with vehicle cream BID) in both of the coprimary endpoints will be tested using a CMH test stratified by baseline EASI score and geographic region. The p-values and overall odds ratio with 95% CI between the ruxolitinib 1.5% cream BID and vehicle cream BID treatment groups will be provided. The p-values will be compared with the 2-sided  $\alpha$  level of 0.05 for each of the coprimary endpoints. A summary of the coprimary endpoints EASI75 and IGA-TS rates will be reported for each treatment group. Stratum-adjusted rate differences (ruxolitinib 1.5% cream BID vs vehicle cream BID) on EASI75 and IGA-TS and the 95% CI will be computed using Mantel-Haenszel weights ([Mantel and Haenszel 1959](#)).

All nonresponders during the VC period, as well as all participants missing the Week 8 assessment and who discontinue study treatment at any time before Week 8, or discontinue from the study for any reason, will be defined as nonresponders for the nonresponder imputation analysis in both coprimary endpoints.

The coprimary endpoints will also be examined for the PP population using the same model as the primary analysis.

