10.4. Statistical Analyses

10.4.1. Primary Analysis

The primary analysis will be based on the ITT population. The primary alternative hypothesis (superiority of ruxolitinib 1.5% cream BID compared with vehicle cream BID) will be tested using a CMH test stratified by baseline EASI score and geographic region. The p-values and overall odds ratio with 95% CI between the ruxolitinib 1.5% cream BID and vehicle cream BID treatment groups will be provided. The p-values will be compared with the 2-sided α level of 0.05. A summary of EASI75 and IGA-TS rates will be reported for each treatment group. Stratum-adjusted rate differences (ruxolitinib 1.5% cream BID vs vehicle cream BID) on EASI75 and IGA-TS and the 95% CI will be computed using Mantel-Haenszel weights ([Mantel and Haenszel 1959](#)).

Participants with missing Week 8 scores for any reason will be defined as nonresponders for the primary analysis. Similar analyses will also be performed in the PP population for the coprimary endpoints. A longitudinal logistic regression with repeated measurements will be performed as a sensitivity analysis. In addition, other missing data imputation methods including multiple imputation and tipping point analysis may be conducted to examine the potential effects of missing data. Subgroup analysis by baseline characteristic (eg, geographic region, age, gender, race, baseline EASI score, season the participant was enrolled, prior cyclosporine therapy, and intertriginous involvement at baseline) will be performed. Details will be provided in the SAP.

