#### **4.1.5. Handling of Missing and Incomplete Data**

In general, values for missing dates will not be handled unless methods for handling missing dates are specified in this section or relevant sections. The original reported dates collected on the eCRF should be used in all relevant listings. The following rules will be used for handling partial dates for analyses requiring dates.

For response endpoints, all nonresponders, as well as all participants who are missing postbaseline values at Week 8, will be defined as nonresponders for the NRI analysis.

For continuous endpoints, any participant who is missing postbaseline values may have missing data handled using MMRM or MI under the missing-at-random assumption. The MMRM model implicitly adjusts for missing data through a variance-covariance structure.

For other endpoints, missing observations will be handled as detailed in the specific sections addressing each analysis.

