#### 7.3.2.1. Primary Estimand

The proportion of participants within each treatment group who achieve the coprimary endpoints, assuming participants with missing Week 8 assessments due to any reasons are nonresponders, will be the primary estimand. The 5 attributes and the strategies associated with the defined intercurrent events are detailed in [Table 4](#).

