**Table 4: Primary Estimand**

Estimand Attribute	Definition		
Treatment effect	Ruxolitinib 1.5% cream BID vs vehicle cream BID		
Population	Participants with moderate AD who had an inadequate response to, or are intolerant to, or contraindicated to TCSs and TCIs (as defined by study inclusion/exclusion criteria)		
Variable	Apply to the coprimary endpoints		
Intercurrent events	Events	Strategy	Rationale (if needed)
	Treatment discontinuation due to any reason	Composite strategy	Participants who discontinue treatment due to any reason prior to Week 8 will be considered as treatment failures (ie, nonresponders) after the intercurrent event. Therefore, composite strategy is used for this type of intercurrent event.
Population-level summary	Stratum-adjusted response proportions difference between–treatment groups		

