## **10. INTERIM ANALYSES**

No formal interim analysis is planned for this study. There are 2 formal planned analyses:

- The primary analysis will occur after the primary database lock, when all participants have completed the VC period (ie, up to Week 8). The sponsor will be unblinded after the primary database lock; however, investigators and participants will remain blinded to the individual study treatment assignment.
- The final analysis will occur when all participants have completed or withdrawn from the study.

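### The nonresponder sentence in SAP 7.3.2 does not match the Week 8 estimand: study exit has no Week 8 limit, and missing data and treatment discontinuation are joined by a conjunction

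*SAP*

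**What the plan says.** The estimand has two limbs, which complement each other.

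- **Missing data.** Protocol 10.4.1: "Participants with missing Week 8 scores for any reason will be defined as nonresponders for the primary analysis". SAP 7.3.2.1 repeats this, "assuming participants with missing Week 8 assessments due to any reasons are nonresponders", and SAP 4.1.5 has a general version: "all participants who are missing postbaseline values at Week 8, will be defined as nonresponders for the NRI analysis".
- **Treatment discontinuation, composite strategy.** SAP Table 4, matching Protocol Table 11: "Participants who discontinue treatment due to any reason prior to Week 8 will be considered as treatment failures". A missing score is not required.

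The operative analysis section, SAP 7.3.2, words the rule differently. After the nonresponders of the VC period, it adds participants "missing the Week 8 assessment and who discontinue study treatment at any time before Week 8, or discontinue from the study for any reason". SAP 7.4.2 applies the same imputation to ITCH4 at Week 8.

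On scope, SAP 7.3.2 opens with "The primary analysis will be based on the ITT population in the VC period". On timing, Protocol 10.6 and SAP 10 place the primary analysis after every participant has finished the VC period. SAP 11.1 lists the changes from the protocol and does not mention the nonresponder rule.

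**The concern.** A programmer will code the responder flag from SAP 7.3.2. As written, the sentence has two faults.

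1. **No Week 8 limit on leaving the study.** The time limit is attached only to stopping treatment. The primary lock waits for the last participant's Week 8 visit, and by then earlier participants can be well into the 16-week extension, from which they may withdraw at any time (Protocol 7.2). Read literally, such a withdrawal overwrites an observed Week 8 response. The Week 8 result would then depend on the lock date, and a rerun at the final analysis could differ.
2. **A conjunction where the estimand has two separate conditions.** The sentence does not reach a participant who misses Week 8 without discontinuing. Nor does it reach one who stops treatment before Week 8 but has a Week 8 value, whom Table 4 calls a failure.

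At stake are the size and reproducibility of the response rates and of the stratum-adjusted difference, which is the estimand's population-level summary.

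**Working it through.** **Inputs.** SAP 3.3 and Table 2 give 225 participants at 2:1 (150 and 75), two-sided alpha 0.05 and Fisher's exact test. Planned rates, ruxolitinib vs vehicle, are EASI75 70% vs 15%, IGA-TS 60% vs 10%, and ITCH4 at Week 8 50% vs 15%. The documents give no discontinuation rate, so every rate in steps 3 and 4 is an assumption.

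**1. Logic of the sentence.** Let M = Week 8 missing, T = treatment stopped before Week 8, S = left the study at any time. The estimand is M or T. The sentence can be bracketed in three ways:

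| Participant | Estimand (M or T) | A: (M and T) or S | B: M and (T or S) | C: M or T or S |
|---|---|---|---|---|
| Responds at Week 8 on treatment, leaves in the extension | Responder | **Nonresponder** | Responder | **Nonresponder** |
| Misses Week 8, stays on treatment and in the study | Nonresponder | **Not covered** | **Not covered** | Nonresponder |
| Stops treatment before Week 8, stays in the study, has a responding Week 8 value | Nonresponder | **Responder** | **Responder** | Nonresponder |
| Stops treatment before Week 8, Week 8 missing | Nonresponder | Nonresponder | Nonresponder | Nonresponder |

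No bracketing reproduces the estimand (departures in bold). Agreement needs both repairs: the conjunction read as a list, and S limited to before Week 8. SAP 4.1.5, 7.3.2.1 and Table 4 supply what the sentence omits (rows 2 and 3). They cannot remove what it adds (row 1), so the missing time limit is the more consequential fault.

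**2. The plan's own figure.** Exact Fisher power over all 151 × 76 outcomes is above 99.9% for EASI75, above 99.9% for IGA-TS and 99.98% for ITCH4 at Week 8. The stated figure of more than 95% is reproduced.

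**3. Study exit without a limit.** If a fraction w of Week 8 responders in each arm leaves before the lock, each rate becomes p × (1 − w) and the difference becomes (p1 − p2) × (1 − w).

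| w (assumed) | EASI75 | Difference | IGA-TS difference | ITCH4 Week 8 difference |
|---|---|---|---|---|
| 0 | 70% vs 15% | 55.0 | 50.0 | 35.0 |
| 4% | 67.2% vs 14.4% | 52.8 | 48.0 | 33.6 |
| 8% | 64.4% vs 13.8% | 50.6 | 46.0 | 32.2 |
| 12% | 61.6% vs 13.2% | 48.4 | 44.0 | 30.8 |

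In counts, 150 × 0.70 = 105 EASI75 responders are planned on ruxolitinib; at w = 10%, 10 or 11 of them would be reclassified. Unequal exit changes the size. Loss of 20% on ruxolitinib and 5% on vehicle gives 0.70 × 0.80 − 0.15 × 0.95 = 0.4175, or 41.8 points. The reverse gives 0.70 × 0.95 − 0.15 × 0.80 = 0.545, or 54.5 points.

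**4. The conjunction.** Suppose a share d of one arm stops treatment before Week 8 but keeps a responding Week 8 value. The difference then moves by d: 2, 5 or 10 points for d = 2%, 5% or 10%, upward if the arm is ruxolitinib and downward if it is vehicle. Equal shares raise both rates and leave the difference unchanged.

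**5. Power.** Rerunning the exact calculation for the two coprimary endpoints, with equal losses of 5% to 20%, unequal losses, and d up to 10%, gives at least 99.99% in every scenario.

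**The case against.** The strongest reply is context. SAP 7.3.2 opens by confining the primary analysis to the VC period, and the disputed sentence itself begins with nonresponders of that period. The VC period ends at Week 8, so leaving the study can be understood as leaving before Week 8. The conjunction can be read as joining items in a list, and under bracketing B the first fault disappears. This is good evidence of what was intended. It does not repair the sentence: the period phrase qualifies only the first group, bracketing B still has the second fault, and the list reading still needs a time limit that is not there. Elsewhere the SAP does use a true conjunction of missing and discontinued, in the multiple imputation section (7.3.4.2), so the list reading cannot be taken for granted.

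A reader might infer that several competing responder definitions are in force. The documents do not support that. The missing-data rule says nothing about discontinuation but does not exclude the composite rule, and SAP 7.3.2.1 and Table 4 put the two together.

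A reader might also infer, from the shared column for Week 8 and ET1 in Protocol Table 3, that early stoppers' scores will routinely be filed as Week 8 data. Protocol 8.8 points the other way: when an ET visit coincides with a scheduled visit, the data go on the ET pages. The SAP has no rule mapping ET data to visits, so a narrow route remains, but no more than that.

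The effect sizes rest on assumed exit rates. That stands in full.

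**Conclusion.** The concern holds as a fault in one operative sentence. SAP 7.3.2, followed as written, does not implement the estimand for either coprimary endpoint or for ITCH4 at Week 8, and SAP 11.1 does not present this as a change. The main risk is that withdrawals during the extension and before the lock overwrite observed Week 8 responses. The omission of early stoppers who have a Week 8 value is real but probably rare.

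If 4% to 12% of Week 8 responders left before the lock, equally in both arms, the EASI75 difference would fall from 55 to between 52.8 and 48.4 points. The fall arises only if the literal reading is programmed. It would therefore go too far to say that the reported effect will be wrong or that the trial's conclusion is threatened: power and significance for the coprimary endpoints are essentially unaffected. The sentence should be corrected before unblinding because it defines the primary endpoint and the correction is cheap.

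**What to change.** Replace the sentence in SAP 7.3.2, and align 4.1.5 and 7.4.2 with it:

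> A participant is a nonresponder at Week 8 if the Week 8 assessment is missing for any reason, or if study treatment was permanently discontinued for any reason before the Week 8 visit (by the recorded date of the discontinuation decision, not the date of last application), whether or not a score was recorded at an ET1 visit. Participants who complete the Week 8 visit on treatment keep their observed Week 8 status; discontinuation of treatment or study at or after that visit does not change it.

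The dating clause is needed because a participant with an IGA of 0 does not apply cream at the Week 8 visit (Protocol Table 3 and 6.1.1). Dated by last application, a cleared participant who stops at Week 8 would look like an early stopper.

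Protocol 7.1.2 names the date of last application and the reason for discontinuation as recorded items. The sponsor should therefore confirm that a decision date is also held. If it is not, the SAP should name the disposition record that decides whether the participant completed the VC period on treatment.

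The cost is SAP wording and that one data check. No visit, assessment or sample size changes. It should be done before the primary database lock.

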#### 7.3.2.1. Primary Estimand

The proportion of participants within each treatment group who achieve the coprimary endpoints, assuming participants with missing Week 8 assessments due to any reasons are nonresponders, will be the primary estimand. The 5 attributes and the strategies associated with the defined intercurrent events are detailed in [Table 4](#).

**Table 4: Primary Estimand**

Estimand Attribute	Definition		
Treatment effect	Ruxolitinib 1.5% cream BID vs vehicle cream BID		
Population	Participants with moderate AD who had an inadequate response to, or are intolerant to, or contraindicated to TCSs and TCIs (as defined by study inclusion/exclusion criteria)		
Variable	Apply to the coprimary endpoints		
Intercurrent events	Events	Strategy	Rationale (if needed)
	Treatment discontinuation due to any reason	Composite strategy	Participants who discontinue treatment due to any reason prior to Week 8 will be considered as treatment failures (ie, nonresponders) after the intercurrent event. Therefore, composite strategy is used for this type of intercurrent event.
Population-level summary	Stratum-adjusted response proportions difference between–treatment groups		

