6.5.2. Criteria for Permanent Discontinuation of Study Cream

Participants must permanently discontinue study cream if they meet any of the following criteria:

- Occurrence of an AE that is related to treatment with the study cream that, in the judgment of the investigator or the medical monitor, compromises the participant's ability to continue study-specific procedures or is considered to not be in the participant's best interest
- Worsening of AD that requires treatment with a prohibited concomitant medication
- Any Grade 4 laboratory abnormality (see [Table 7](#)) considered related to the study cream
- Persistent AE requiring an interruption of study cream for more than 2 weeks without resolution of the AE

See Section [7](#) for discontinuation procedures.

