6.6.3. Restricted Medications and Procedures

The following are permitted during the study under specified conditions:

- Short-term use of systemic corticosteroids may be permitted to treat acute AEs (eg, asthma) during the VCE period, and the decision to keep the participant in the study (or to permanently discontinue study cream) will be made in consultation with the medical monitor and sponsor.
- Participants may continue using sedating antihistaminic drugs, as long as their use is part of a pre-existing, well-established, and stable treatment regimen, 2 weeks prior to Day 1 and throughout the first 8 weeks of study. There are no restrictions for use of nonsedating antihistamines.
- Use of any over-the-counter, nonprescription preparations deemed acceptable by the investigator is permitted under an established and stable treatment regimen 2 weeks prior to Day 1 and throughout the first 8 weeks of the study.
- Use of any prescription medication (including phytotherapeutic, herbal, or plant-derived preparations) within 2 weeks before Day 1 through the safety follow-up visit is allowed if deemed acceptable by the investigator.
- Immunizations with a live-attenuated vaccine are not recommended during the VC and VCE periods unless deemed necessary by the investigator.
- Allergen immunotherapy (desensitization) that is ongoing at a stable dose at the time of study entry may be continued while on study but only at the same dose throughout the first 8 weeks of the study.
- Bleach baths are allowed as long as they do not exceed 2 baths per week and their frequency remains the same throughout the first 8 weeks of the study.
- Topical anti-infectives or other topical treatments applied to active AD lesions should not be used for at least 4 hours before and 2 hours after application of study cream.

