6.6.4. Prohibited Medications and Procedures

The following are not permitted during screening or the VC/VCE periods:

- Any investigational medication other than the study cream
- Any of the following topical treatments: corticosteroids, calcineurin inhibitors, PDE4 inhibitors, or aryl hydrocarbon receptor–modulating agents
- Other topical agents for treatment of AD (except bland emollients as noted in Section [6.6.2](#))
- Treatment known to affect the course of AD
- Systemic corticosteroids, methotrexate, cyclosporin A, azathioprine, biologic therapies, or other immunosuppressant agents
- Phototherapy or tanning beds
- Strong systemic CYP3A4 inhibitors

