10.4.1.1. Primary Estimand

The proportion of participants within each treatment group who achieve the coprimary endpoints, assuming participants with missing Week 8 assessments due to any reasons are nonresponders, will be the primary estimand. The 5 attributes and the strategies associated with the defined intercurrent events are detailed in [Table 11](#).

Table 11: Primary Estimand

Estimand Attribute	Definition		
Treatment effect	Ruxolitinib 1.5% cream BID vs vehicle cream BID		
Population	Participants with moderate AD who had an inadequate response to, or are intolerant to, or contraindicated to TCSs and TCIs (as defined by study inclusion/exclusion criteria)		
Variable	Apply to the coprimary endpoints		
Intercurrent events	Events	Strategy	Rationale (if needed)
	Treatment discontinuation due to any reason	Composite strategy	Participants who discontinue treatment due to any reason prior to Week 8 will be considered as treatment failures (ie, nonresponders) after the intercurrent event. Therefore, composite strategy is used for this type of intercurrent event.
Population-level summary	Stratum-adjusted response proportions difference between–treatment groups		

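### The primary estimand has no strategy for prohibited AD therapy used before Week 8 by participants who stay on study cream

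*SAP*

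**What the plan says.** SAP Table 4 and Protocol Table 11 each contain one intercurrent event, "Treatment discontinuation due to any reason", with a composite strategy. The rationale in Protocol 10.4.1.1 is that "Participants who discontinue treatment due to any reason prior to Week 8 will be considered as treatment failures".

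The rules that assign nonresponse are of the same kind:

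- Protocol 10.4.1: "Participants with missing Week 8 scores for any reason will be defined as nonresponders for the primary analysis".
- SAP 7.3.2: observed nonresponders, "all participants missing the Week 8 assessment and who discontinue study treatment at any time before Week 8", and those who leave the study.
- SAP 7.3.4.2 (multiple imputation): the override to nonresponse applies to missing assessments after discontinuation for lack of efficacy or an adverse event.

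On medication, Protocol 6.6.4 bars, during screening and both treatment periods, "Any of the following topical treatments: corticosteroids, calcineurin inhibitors, PDE4 inhibitors" and other topical AD agents, as well as systemic immunosuppressants, biologics and phototherapy. Protocol 6.5.2 makes discontinuation of study cream mandatory for "Worsening of AD that requires treatment with a prohibited concomitant medication". SAP 6.3 says that deviations such as "use of prohibited concomitant medications, will be reviewed", and that decisions on exclusion from the PP population are taken before unblinding.

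**The concern.** Under the composite strategy, giving up the assigned cream counts as failure. Continuing the cream and adding a prohibited AD treatment can count as success, because no rule resets that participant's Week 8 result. The same applies to ITCH4 at Week 8, which SAP 7.4.2 handles with the nonresponder method of the primary analysis.

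At stake is what the response rates, rate difference and odds ratio in SAP 7.3.2 describe: the effect of the assigned cream, or the effect of the cream plus whatever else was taken. If no strategy is fixed in advance, the first decision on how to count such participants may be made once their results are known.

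**Working it through.** **Step 1. Which routes lead to nonresponse?**

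| Situation before Week 8 | Provision | Result in ITT primary analysis |
|---|---|---|
| Worsening AD requires a prohibited drug | Protocol 6.5.2: cream must stop | Nonresponder, through discontinuation |
| AD to be treated exceeds 20% BSA | Protocol 7.1.1: cream must stop | Nonresponder, through discontinuation |
| Prohibited AD therapy by self-medication or prescribed elsewhere, cream continued | SAP 6.3: deviation review, possible PP exclusion | Observed Week 8 result |
| Prohibited drug for another condition (e.g. systemic corticosteroid for an AE), cream continued | SAP 6.3, as above | Observed Week 8 result |

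The mandatory discontinuation list in Protocol 7.1.1 does not name use of prohibited medication as such. The gap is therefore the last two rows.

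**Step 2. Reproduce the planned power.** Inputs from SAP 3.3 and Table 2: 225 participants randomized 2:1 (150 ruxolitinib, 75 vehicle), Fisher exact test, two-sided 0.05. Enumerating both binomial distributions gives more than 99.9% for EASI75 (70% vs 15%), more than 99.9% for IGA-TS (60% vs 10%) and 99.98% for ITCH4 at Week 8 (50% vs 15%). The stated figures above 95% are confirmed.

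**Step 3. Effect on the difference and on power.** Usage is not given, so the shares below are assumed. Take the Table 2 rates as the rates with users counted as nonresponders. Then add a share of each arm counted as responders only because of prohibited therapy.

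| Added share, ruxolitinib / vehicle | EASI75 difference (55 without users) | IGA-TS difference (50 without users) |
|---|---|---|
| 0 / 5% | 50 | 45 |
| 0 / 10% | 45 | 40 |
| 0 / 20% | 35 | 30 |
| 5% / 5% | 55 | 50 |
| 5% / 0 | 60 | 55 |
| 10% / 0 | 65 | 60 |

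The lowest powers occur with 20% in vehicle alone: 99.88% for EASI75 and 99.12% for IGA-TS. Even there, the chance of winning on both is at least 100 - 0.12 - 0.88 = 99.0%. Suppose instead that the planning rates already include such responders, and 5%, 10% or 20% are removed from ruxolitinib alone. Power then stays above 99.9%. These scenarios were run for the coprimary endpoints only, not for ITCH4.

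**Step 4. A more plausible size for the vehicle arm.** Assume that 2-8% of 75 participants use prohibited AD therapy and continue the cream (75 × 0.02 = 1.5 to 75 × 0.08 = 6 people), and that 50% of them reach EASI75.

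- Change in the vehicle rate = usage × (response among users - response they would have had anyway).
- If 15% would have responded anyway (the planning rate): 0.02 × (0.50 - 0.15) = 0.7 points, to 0.08 × (0.50 - 0.15) = 2.8 points.
- If none would have responded anyway: 0.02 × 0.50 = 1 point, to 0.08 × 0.50 = 4 points.
- Crude EASI75 odds ratio with ruxolitinib at 70%: (0.70/0.30)/(0.15/0.85) = 13.2. With vehicle at 17.8% it is (0.70/0.30)/(0.178/0.822) = 10.8. With vehicle at 19% it is (0.70/0.30)/(0.19/0.81) = 9.9.

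**Step 5. What a composite rule removes.** It resets every responding user, so the vehicle rate falls by the full 1-4 points. With a 15% background, 0.02 × 0.15 = 0.3 to 0.08 × 0.15 = 1.2 points of that are people who would have responded without the extra therapy.

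**The case against.** The strongest reply is that the main route is already closed. Rescue for worsening disease forces discontinuation, and discontinuation is nonresponse. Protocol 6.4 has staff ask about additional topical, systemic and over-the-counter products. SAP 6.6 and planned Table 1.4.3.4 show AD concomitant medication by arm for the VC period. Both coprimary endpoints are repeated in the PP population. All of this is true, and it confines the gap to use with cream continued. It does not close the gap: PP exclusion is case by case, drops the participant rather than counting a failure, and leaves the primary result unchanged.

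Several stronger readings are tempting but unsupported:

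- **Rescue in general is credited to the cream.** Protocol 6.5.2 rules this out for worsening AD that requires a prohibited drug.
- **The bias runs toward the null because vehicle participants use more rescue.** Neither document gives usage by arm. Use on ruxolitinib may enlarge the difference.
- **Half of users reaching EASI75 is a known figure.** It is an assumption, and perhaps a generous one for topical rescue, since Protocol 5.1 enrols people with inadequate response, intolerance or contraindication to TCSs and TCIs.
- **Every prohibited drug signals failure of the cream.** A systemic corticosteroid for asthma does not.
- **Protocol 6.6.3 permits AD rescue.** It sets timing only: "Topical anti-infectives or other topical treatments applied to active AD lesions should not be used for at least 4 hours before" and for a period after study cream. A topical product placed on a lesion need not be an AD treatment. Read beside the ban in 6.6.4 on other topical AD agents, however, the boundary is unclear.

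**Conclusion.** The gap is real and narrow. Prohibited AD therapy before Week 8 with study cream continued has no estimand strategy and no nonresponder trigger, so such participants keep their observed result in the primary analysis.

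The consequence is for interpretation and the size of the estimate. On the assumptions in Step 4, the vehicle EASI75 rate rises by about 0.7-2.8 points; 1-4 points applies only if no user would otherwise have responded. A reader might infer that the superiority test is at risk. With planned differences of 50-55 points it is not, even when 20% of the vehicle arm responds only through prohibited therapy. The usage range, the response among users and their background response are all assumptions. The wording gap itself does not depend on them. This is a worthwhile, inexpensive correction and not a threat to the trial's validity.

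**What to change.** 1. Add a second intercurrent event to SAP Table 4 and Protocol Table 11: use, before the Week 8 assessment, of a therapy prohibited in Protocol 6.6.4 and taken to treat AD; composite strategy, nonresponder.
2. Add the same trigger to the nonresponder rule in SAP 7.3.2, so that it reaches Week 8 ITCH4 through SAP 7.4.2. At the same time, align that rule with Table 4: it joins a missing Week 8 assessment and discontinuation with an *and*, whereas Table 4 makes discontinuation sufficient by itself.
3. Identify cases by blinded review of the AD concomitant medications behind Table 1.4.3.4, against a prespecified medication list, before the primary database lock.
4. Handle prohibited drugs taken for a non-AD condition in a sensitivity analysis. Keep the current rule as a further sensitivity analysis.
5. Reconcile Protocol 6.6.3 with 6.6.4 on other topical treatments applied to active lesions, so that cases can be classified consistently.

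The cost is wording in both documents and one blinded review of data already collected. The downside is slightly lower response rates: some users who would have responded anyway are counted as failures (0.3-1.2 points of the vehicle arm on the Step 5 assumptions). On ruxolitinib, where the planning rate is 70%, genuine responders could also be reclassified, which is why the current rule should stay as a sensitivity analysis.
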